#### **4.3 Exclusion Criteria**

##### **1. Disease Target Exclusion**

- a. Subject has a structural lesion on neuroimaging, other than vascular compression of the trigeminal nerve or nerve root that would explain the neuralgia
- b. Subject has a clinically evident neurologic deficit on neurologic examination of the cranial nerves (other than mild sensory changes in the distribution of the affected trigeminal nerve).
- c. Subjects who have undergone rhizotomy of the trigeminal ganglion or nerve root (including radiofrequency ablation and glycerol injection) gamma knife surgery, or microvascular decompression surgery for the treatment of trigeminal neuralgia should be discussed with the Biohaven Medical Monitor on a case by case basis.

2. Medical History and Concurrent Diseases

- a. Subjects history of HIV disease
- b. Subject history with current evidence of uncontrolled, unstable or recently diagnosed cardiovascular disease, such as ischemic heart disease, coronary artery vasospasm, and cerebral ischemia. Subjects with Myocardial Infarction (MI), Acute Coronary Syndrome (ACS), Percutaneous Coronary Intervention (PCI), cardiac surgery, stroke or transient focal neurological deficit during the 6 months prior to screening
- c. Uncontrolled hypertension (high blood pressure) at screening (e.g., repeated diastolic measurement of  $\geq 96\text{mmHg}$ )
- d. Subject has a current diagnosis of major depression which is not related to current TN diagnosis, other pain syndromes, psychiatric conditions (e.g., schizophrenia), dementia, or significant neurological disorders (other than migraine) that, in the Investigator's opinion, might interfere with study assessments
- e. Subject has a history of gastric, or small intestinal surgery (including Gastric Bypass, Gastric Banding, Gastric Sleeve, Gastric Balloon, etc.), or has a disease that causes malabsorption
- f. Subject has a history or diagnosis of Gilbert's Syndrome or any other active hepatic or biliary disorder
- g. The subject has a history or current evidence of any significant and/or unstable medical conditions (e.g., history of congenital heart disease or arrhythmia, known suspected infection, hepatitis B or C, or cancer) that, in the investigator's opinion, would expose them to undue risk of a significant adverse event (AE) or interfere with assessments of safety or efficacy during the course of the trial
- h. History of, treatment for, or evidence of, alcohol or drug abuse within the past 12 months or subjects who have met DSM-V criteria for any significant substance use disorder within the past 12 months from the date of the screening visit

- i. Subjects should be excluded if they have a positive drug screen for drugs of abuse that in the investigator's judgment is medically significant, in that it would impact the safety of the subject or the interpretation of the study results. In addition:
  - (1) Detectable levels of cocaine, amphetamine, and phencyclidine (PCP) in the drug screen are exclusionary. Subjects who are positive for amphetamines, and who are on a prescribed amphetamine medication for an approved indication (e.g. ADHD) will be allowed into the study at the Investigator's discretion. This determination by the Investigator must be well documented in the subject's source medical records. The stimulant dose must be stable 4 weeks from prior to randomization visit until the end of treatment visit occurs.
  - (2) Detectable levels of marijuana in the drug screen are not exclusionary, if in the investigator's documented opinion the subject does not meet DSM-V criteria  for substance use disorder, and the positive test does not signal a clinical condition that would impact the safety of the subject or interpretation of the study results.
- j. Hematologic or solid malignancy diagnosis within 5 years prior to screening. Subjects with a history of localized basal cell or squamous cell skin cancer are eligible for the study if they are cancer-free prior to the screening visit in this study.
- k. Body mass index  $\geq 33.0 \text{ kg/m}^2$
- l. History of gallstones or cholecystectomy

3. Allergies and Adverse Drug Reactions

- a. History of drug or other allergy which, in the opinion of the principal investigator, makes the subject unsuitable for participation in the study.

4. Sex and Reproductive Status

- a. Females of child-bearing potential who are unwilling or unable to use an acceptable contraceptive method or abstinence to avoid pregnancy for the entire study period and for 56 days after the study.
- b. Women who are pregnant or breastfeeding. Women with a positive pregnancy test on enrollment or prior to study drug/medication administration.

5. ECG and Laboratory Test Findings

- a. Estimated glomerular filtration rate (eGFR) according to the re-expressed abbreviated (four-variable) Modification of Diet in Renal Disease (MDRD) Study equation  $\leq 40 \text{ ml/min}/1.73 \text{ m}^2$
- b. Corrected QT interval  $> 470 \text{ msec}$  (QTc by method of Frederica), at Screening

- c. Left Bundle Branch block
- d. Right Bundle Branch Block with a QRS duration  $\geq$  150 msec.
- e. Intraventricular Conduction Defect with a QRS duration  $\geq$  150 msec.
- f. Serum bilirubin (Total, Direct or Indirect)  $> 1 \times$  ULN (Only abnormal values of between 1-1.5x ULN may be repeated once for confirmation during the screening period)
- g. HbA1C  $\geq 8.0\%$  at screening
- h. AST (SGOT) or ALT (SGPT)  $> 1 \times$  ULN (Only abnormal values of between 1-1.5x ULN may be repeated once for confirmation during the screening period)
- i. GGT  $> 1.5 \times$  ULN (Abnormal values  $> 1.5 \times$  ULN may be repeated once for confirmation during the screening period)
- j. Neutrophil count  $\leq 1000/\mu\text{L}$  (or equivalent).

## 6. Other Exclusion Criteria

- a. Prisoners or subjects who are involuntarily incarcerated
- b. Subjects who are compulsorily detained for treatment of either a psychiatric or physical (e.g., infectious disease) illness
- c. Non-compliance with or inability to complete the Paper Diary during the Screening Period. Non-compliance is 2 or more missed evening reports during the Screening Phase. Subjects should be considered for discontinuation after discussion with the sponsor.
- d. Participation in clinical trial with non-biological investigational agents or investigational interventional treatments within the 30 days prior to Baseline Visit
- e. Subjects who have previously participated in any BHV-3000/ BMS-927711/ rimegepant study within the last 2 years
- f. Participation in clinical trial with biological investigational agents within the 90 days prior to Baseline visit
- g. Score of  $> 1$  ("a little") on Question 2 on the Sheehan Suicidality Tracking Scale for the period of 30 days prior to screening and during the study. All other questions must be scored a "0" ("Not at all"). Please see section [5.2.8](#) for additional guidance on study discontinuation based on results from the S-STS
- h. Participation in any other investigational clinical trial while participating in this clinical trial
- i. Please see section [4.4](#) for Prohibited medications and section [5.3.5](#) for allowable rescue medications

j. Subjects who were considered screen failures from BHV3000-202 may be considered for re-screening provided the ineligibility was due to one of the eligibility items adjusted in Amendment 04, Protocol Version 5. BMI less than 33.0 kg/m^2 (previously BMI less than or equal to 30kg/m^2). Stable dose of 4 weeks prior to randomization visit (previously 3 month prior to screening and/or randomization visit). Subjects who were considered screen failures from BHV3000-202 for other reasons should be discussed with the Sponsor and approval must be granted prior to re-screening. Adequate documentation in source records must support the previously failed criteria.

#### **4.4 Prohibited Concomitant Medication**

The below medications are prohibited prior to randomization and during the course of this study or as specified.

1. St. John's Wort should not be taken 14 days prior to randomization and throughout the study.
2. Barbiturate-containing products (e.g. Fioricet, Fiorinal, butalbital, phenobarbital) should not be taken 14 days prior to randomization and throughout the study.
3. Modafinil (PROVIGIL®) should not be taken 14 days prior to randomization and throughout the study.
4. Butterbur root or extracts should not be taken 14 days prior to randomization and throughout the study.
5. History of use of ergotamine medications on greater than/equal 10 days per month on a regular basis for greater than/equal 3 months.
6. Use of narcotic medication, such as opioids (e.g. morphine, codeine, oxycodone and hydrocodone) for at least 2 days prior to randomization.
7. Use of all acetaminophen or acetaminophen containing products must be discontinued at least 2 days prior to randomization (acetaminophen < 1000 mg/day is allowed as rescue medication, see Section 5.3.5). During the screening phase (14 to 30 days) use of acetaminophen or acetaminophen containing products at daily dosing levels of greater than 1000 mg/day is prohibited.
8. Use of marijuana is prohibited during the study.
9. Muscle relaxants are prohibited during the study. The use of baclofen is permitted, provided that patients are on stable dosing for at least 8 weeks prior to their randomization visit.
10. Concomitant use of strong CYP3A4 inhibitors with rimegepant is prohibited during the study. If use of a strong CYP3A4 inhibitor is required, such as use of HIV Protease Inhibitors, Hepatitis C protease inhibitors, certain azole antifungals, or clarithromycin, dosing with rimegepant should be stopped. Please see section 17, [Appendix 2](#).

11. Concomitant use of strong CYP3A4 inducers with rimegepant is prohibited during the study. Therefore, the use of carbamazepine during this study will be prohibited. However, patients taking oxcarbazepine for the treatment of their trigeminal neuralgia may continue with their current therapy, provided they have been on stable dosing for at least 4 weeks prior to their randomization visit. Patients on carbamazepine may be transitioned to oxcarbazepine. Similarly, these patients must be on stable doses of oxcarbazepine for at least 4 weeks prior to the randomization visit. Please see section [17, Appendix 2](#).
12. Concomitant use of strong inhibitors of the P-gp transporter with rimegepant is prohibited during the study. Please see section [17, Appendix 2](#).
13. The use of CGRP antagonists (biologic [e.g. AimovigTM and AjovyTM] or small molecule) other than rimegepant.

#### **4.4.1 Trigeminal Neuralgia Medications**

Throughout the study, patients will be permitted to use Standard of Care Trigeminal Neuralgia medications, with the exception of carbamazepine, including rescue medications, provided that these medications have been used at stable dosing for at least 4 weeks prior to randomization visit. Use of these concomitant medications will be recorded daily by the subject on a paper diary and reported to the site.

#### **4.5 Women of Childbearing Potential**

Women of childbearing potential (WOCBP) include any female who has experienced menarche and who has not undergone successful surgical sterilization (hysterectomy, bilateral tubal ligation, or bilateral oophorectomy) or is not postmenopausal. Post menopause is defined as:

- Amenorrhea greater than or equal to 12 consecutive months without another cause and a documented serum follicle stimulating hormone (FSH) level  $> 35\text{mIU/mL}$  or
- Woman with irregular menstrual periods and a documented serum follicle stimulating hormone (FSH) level  $> 35\text{mIU/mL}$  or

NOTE: FSH level testing is not required for women greater than or equal to 62 years old with amenorrhea of greater than or equal to one year

- Woman on hormone replacement therapy (HRT)

Women of childbearing potential (WOCBP) with male partners and men with women partners of childbearing potential must be using two acceptable methods of contraception to avoid pregnancy throughout the study and for up to 56 days after the last dose of investigational product in such a manner that risk of pregnancy is minimized. It is required that all WOCBP use two methods of contraception for the duration of the study (i.e. beginning before treatment with the 1 dose of study drug/medication to 56 days after dosing). The two methods should include one barrier method (i.e. . condom with spermicidal gel, intrauterine devices, cervical cap etc.) and one other method. The other method could include oral contraceptives or another barrier method (note, an Intra Uterine Device is considered one method). Subjects should not take

Investigational Study drug/medication if they are pregnant and subject should immediately contact Study Investigator.

#### **4.6 Deviation from Inclusion/Exclusion Criteria**

Any significant event that does not comply with the inclusion exclusion criteria, study conduct, or study procedures will be documented as a deviation. Deviations will be documented and reported through the clinical monitoring of the trial. Clinically significant deviations will be reported to the IRB/EC at the frequency required by your IRB/EC. There will be no protocol exceptions granted by the Sponsor for Inclusion/Exclusion criteria.

## 5 STUDY CONDUCT

### 5.1 Study Materials

The sponsor will provide investigational product which will include BHV-3000 (75 mg) IR tablets, ODT, and matching placebo.

The site will also be provided with a Regulatory binder, and IWRS Manual. Instructions on all specimens collected, as well as Laboratory Kits and Laboratory Manual will be provided by a central laboratory.

The following materials will also be provided at study start:

- Daily paper diaries for recording average daily pain, worst pain episode, record concomitant medication and procedures, rescue medications, and study drug/medications.
- Pharmacy Binder
- Drug Accountability Logs
- Rating Scales
- Investigator Brochure
- Serious Adverse Event (SAE) Forms
- Pregnancy Surveillance Forms
- Sheehan Suicidality Tracking Scale (S-STS)

The site will use a Paper Data Capture tool to submit study data. Case Report Forms (CRFs) will be prepared for all data collections including Serious Adverse Event (SAE) Reporting.

Sites will be provided with a Biohaven approved protocol and any amendments.

The investigator will be required to have a centrifuge, a secure locked cabinet or similar (for drug storage) as well as appropriate containers and dry ice for shipment and storage of blood and plasma samples. Enough dry ice, when indicated, should be utilized to allow samples to arrive at their designated laboratory in a frozen state.

### 5.2 Safety Assessments

#### 5.2.1 ***Vital Signs and Physical Measurements (Height and Weight)***

Sitting vital sign measurements (temperature, blood pressure, respiration rate, and heart rate) will be recorded during the scheduled visits as specified in the Schedule of Assessments/Time & Events and as medically necessary.

Body weight and height will be recorded at scheduled visits, per the Schedule of Assessments.

### **5.2.2      *Electrocardiogram (ECG)***

A 12-Lead ECG will be recorded during the scheduled visits as specified in the Schedule of Assessments/Time & Events and as medically necessary.

### **5.2.3      *Physical Exam***

Subjects will undergo a complete physical exam during the screening phase and at the follow up visit at the end of the study. The Physical Exam should include at least the following components: HEENT (head, eyes, ears, nose, and throat), neck, lymph nodes, lungs, cardiovascular, abdomen, skin, and musculoskeletal evaluation by the Principal Investigator or a medically qualified delegate. If a subject is discontinued for any reason, an attempt should be made to conduct a final physical exam.

### **5.2.4      *Neurologic Exam***

Subjects should undergo a routine neurologic exam at the screening visit. Any abnormal neurological deficit on cranial nerve examination, other than mild sensory changes in the affected trigeminal nerve, that is not consistent with a Trigeminal Neuralgia diagnosis should exclude the subject from participation.

### **5.2.5      *Neuroimaging***

Subjects should have neuroimaging prior to randomization to rule out structural lesions other than vascular compression of the trigeminal nerve or nerve root. This can include prior imaging that occurred during the patient's diagnostic work-up for trigeminal neuralgia. The patient must provide the results of this imaging to the site. If no neuroimaging is provided by the subject during the screening phase, an MRI should be done at the site prior to randomization.

### **5.2.6      *Laboratory Assessments***

Laboratory testing will include the following:

1. Hematology: hemoglobin, hematocrit, platelets, CBC with differential and absolute neutrophil count
2. Serum Chemistry: sodium, potassium, chloride, calcium, ALT, AST, LDH, alkaline phosphatase, GGT, phosphorous, bicarbonate, CPK, total protein, albumin, total bilirubin (if greater than 2 mg/dl bilirubin will be fractionated), glucose, creatinine, BUN, uric acid, and pregnancy testing (WOCBP). Additionally, at screening, total cholesterol, LDL, HDL, triglycerides, folate, HbA1C, P-Amylase or Lipase, TSH, and T4;
3. Estimated glomerular filtration rate (eGFR) using the estimated MDRD formula will be calculated and reported at each visit that clinical laboratory tests are collected as outlined in the Schedule of Assessments;

4. Urinalysis: macroscopic examination, pH, specific gravity, ketones, nitrites, urobilinogen, leukocyte esterase, protein, glucose, and occult blood will be performed during the scheduled visits as specified in the Schedule of Assessments/Time & Events and as medically necessary. If blood, protein, or leukocytes, are positive microscopic examination will be performed on abnormal findings;
5. Serum pregnancy test will be conducted at screening and baseline visits. Urine pregnancy tests will be performed prior to dosing at Baseline and at scheduled visits, at study visits where lab assessments are not performed, or at the discretion of the Investigator;
6. HBsAg, HCV, HIV antibody detection will be performed at screening.
7. Urine Drug Screen for drugs of abuse will be conducted as outlined in the Schedule of Assessments ([Table 1](#)).

Any lab value outside of the normal range must be brought to the attention of a physician (Investigator or Sub-Investigator) at the site. The Investigator will indicate whether or not a flagged value is of clinical significance. In addition, if warranted repeat labs can be drawn.

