**Table 1: Schedule of Assessments Double- Blind Phase**

Procedure	Screening (a) Visit	Baseline (Randomization) (Day 1) (i)	Day 14 (+/- 2 days)	Day 21 (+/- 2 days)	Day 35 (-2/+5 days) (i)
	Visit 1	Visit 2	Visit 3	Visit 4	Visit 5
Informed Consent	X				
Inclusion/Exclusion Criteria	X	X			
Medical History	X				
Neuroimaging (a)	X				
Neurologic Exam	X				
Concomitant Medications and Procedure Review (b)	X	X	X	X	X
Physical Exam	X				X
Vital signs/physical measurements (d)	X	X	X	X	X
Laboratory Assessments	X	X			X
Liver Function Tests	X	X	X		X
Serology (HBsAg, HCV, HIV)	X				
Pregnancy Test (Serum)	X	X			
Pregnancy Test (Urine)		X			X
Urine Drug Screen	X				X
12-Lead ECG	X	X	X		X
Serious Adverse Event Assessment (e)	X	X	X	X	X
Sheehan Suicidality Tracking Scale (S-STS)	X	X	X	X	X
Daily Average Pain (NPRS) (h)	X	X	X	X	X
Patient Global Impression Change Scale (PGI-C)			X	X	X

Procedure	Screening (o) Visit	Baseline (Randomization) (Day 1) (i)	Day 14 (+/- 2 days)	Day 21 (+/- 2 days)	Day 35 (-2/+5 days) (i)
	Visit 1	Visit 2	Visit 3	Visit 4	Visit 5
Pain Disability Index		X	X	X	X
Penn Facial Pain Scale-Revised		X	X	X	X
Record of Daily Rescue Medications		X	X	X	X
Daily Worst Pain (NPRS)	X	X	X	X	X
CCI					
Randomization (c)(g)		X			
Dispense Study Drug/Medication (l)		X	X	X	X (l)
Study Drug/Medication Accountability (f)		X	X	X	X
Paper Diaries Dispensed (m)	X	X			X (m)
Pain Paper Diary returned/reviewed for completeness		X	X	X	X

(a) Subjects must have at least one neuroimaging study (MRI) completed any time prior to randomization. For patients with a strong contraindication to MRI (eg, pacemaker), CT scan, preferably with CTA, will be allowed based on approval by the medical monitor.

(b) Concomitant medications, including standard of care Trigeminal Neuralgia medications, taken during the screening period and rescue medications taken during the double-blind treatment period and open-label extension should be recorded on the subject's paper diary and reviewed by study personnel at each visit.

(c) The actual baseline visit date should be used for IWRS enrollment date.

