### **3.5.2      Randomization Phase (35 Days)**

Patients with a mean score of greater than or equal to 4 on the daily “average intensity” 11 point Numeric Pain Rating Scale, during the 14 to 30 day screening period, will be randomized to one of two treatment sequences to receive BHV-3000 (75 mg QD) administered orally vs placebo (QD) in a 1:1 ratio. Patients should be encouraged to take their dose of medication in the mornings. Patients with a diagnosis of typical and atypical TN will be stratified equally into the two sequences; and patients with atypical TN will not exceed 50% of the subjects. Each sequence will include a 2 week treatment phase, with daily dosing of study drug/medication or placebo. This will be followed by a 7 day placebo washout period. After the placebo washout period, another 2 week treatment phase will follow, again with once daily dosing of study drug/medication or placebo. In the first sequence, patients will receive placebo for the first treatment period and BHV-3000 75 mg during the second treatment period. The second sequence will have BHV-3000 75 mg during the first 2 week treatment period, followed by placebo in the second treatment phase.

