- c. No clinically significant abnormality identified on the medical or laboratory evaluation. A subject with a clinical abnormality or laboratory parameters outside the reference range may be included only if the investigator considers that the finding is not clinically significant and will not introduce additional risk factors and will not interfere with the study procedures
- d. At the Baseline Visit prior to dispensing Investigational Study drug/medication, WOCBP must have a negative urine pregnancy test
- e. Women must not be breastfeeding

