### **6.2.2 Selection and Timing of Dose Administration**

During the Double-Blind Phase of the study, subjects will be randomized to a sequence of either rimegepant (75 mg QD) and then placebo or placebo then rimegepant (75 mg QD) in a 2-sequence, 2-period, crossover design. Study drug/medication will be dispensed at the baseline visit and at Days 14 and 21. Subjects should take the first dose the day of the baseline visit. Study drug/medication should be administered in the morning without regard to meals. Subjects who showed continued compliance during the Double-Blind Phase may choose to enter a 12 week Open-label Extension Phase with daily dosing of rimegepant (75 mg QD) ODT. Open-label study drug/medication will be dispensed at Day 35 visit for subjects who enter the Open-label Extension Phase. Subjects should take the first dose of OLE study drug/medication on Day 36.

During the Open-label Extension Phase, if a dose of study drug/medication for a given day is missed, lost, or otherwise unable to be taken, the subject should document that as a missed dose on the **subject paper study log**.

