6.4.2 Laboratory Tests

Laboratory tests of clinical interest are collected at the following visits:

- Hematology: Screening, Baseline (Day 1), Day 35, Day 119, Follow-up safety visit (14 days post last dose) and early termination
- Serum chemistry: Screening, Baseline (Day 1), Day 35, Day 119, Follow-up safety visit (14 days post last dose) and early termination. Exceptions are for the following:
 - Liver function Tests (LFTs) (ALT, AST, ALP, TBL, direct bilirubin, indirect bilirubin): All visits except Day 21
 - Lipids (total cholesterol, high-density lipoprotein [HDL] cholesterol, low-density lipoprotein [LDL] cholesterol, triglycerides), folate, HbA1C, P-Amylase or Lipase, TSH, and T4: Screening
- Urinalysis: Screening, Baseline (Day 1), Day 35, Day 119, Follow-up safety visit (14 days post last dose) and early termination.

Laboratory tests of clinical interest for analyses include the following:

- Hematology: hemoglobin, hematocrit, platelets, CBC with differential and absolute neutrophil count
- Serum chemistry: sodium, potassium, chloride, calcium, ALT, AST, LDH, alkaline phosphatase, GGT, phosphorous, bicarbonate, CPK, total protein, albumin, total bilirubin, glucose, creatinine, BUN, uric acid, total cholesterol, LDL, HDL, triglycerides, folate, HbA1C, P-Amylase or Lipase, TSH, and T4
- Urinalysis: macroscopic examination, pH, specific gravity, ketones, nitrites, urobilinogen, leukocyte esterase, protein, glucose, and occult blood.
- LFTs: ALT, AST, TBL and ALP

Refer to the Core SAP for toxicity grading.

Estimated glomerular filtration rate (eGFR) will be derived using the modification of diet in renal disease (MDRD) formula; refer to the Core SAP for additional details.

TLFs will be provided to show data in Systeme Internationale (SI) unit system.

A by-subject listing of the following select laboratory tests will be provided for enrolled subjects with at least one laboratory assessment of grade 3 or 4 abnormality or a positive pregnancy test result: hematology; serum chemistry (including eGFR derived using MDRD); urinalysis. If there is a positive pregnancy test, defined as a serum or urine pregnancy test with either (1) “positive” character value, or (2) numeric value ≥ 25 U/L. The listing will also include all pregnancy test results over time.

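### Table 1 schedules no pregnancy test at Day 21, although Protocol 5.2.6 calls for a urine test at visits without lab assessments and placebo-first women start rimegepant at that visit

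*Protocol*

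**What the plan says.** **The text rule.** Protocol 5.2.6, item 5, states: "Urine pregnancy tests will be performed prior to dosing at Baseline and at scheduled visits, at study visits where lab assessments are not performed". The sentence ends by also allowing tests at the investigator's discretion. Item 5 places the serum tests at screening and baseline.

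**The double-blind schedule.** In Table 1, the row beginning "Pregnancy Test (Urine" is marked at Baseline and Day 35 only. The serum row is marked at Screening and Baseline only. At Day 21 the Laboratory Assessments and Liver Function Tests rows are both blank.

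**The SAP's visit lists.** SAP 6.4.2 agrees with Table 1. For blood counts it gives "Hematology: Screening, Baseline (Day 1), Day 35, Day 119, Follow-up safety visit (14 days post last dose) and early termination", and for liver tests "Liver function Tests (LFTs) (ALT, AST, ALP, TBL, direct bilirubin, indirect bilirubin): All visits except Day 21".

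**Dispensing.** Protocol 6.2.2: "Study drug/medication will be dispensed at the baseline visit and at Days 14 and 21". Protocol 3.5.2: "In the first sequence, patients will receive placebo for the first treatment period and BHV-3000 75 mg during the second treatment period". SAP 6.4.1.3 opens the second on-treatment period at the first dose on the Day 21 visit.

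**Eligibility.** Inclusion 3d (Protocol 4.2): "At the Baseline Visit prior to dispensing Investigational Study drug/medication, WOCBP must have a negative urine pregnancy test". Exclusion 4b (Protocol 4.3) bars "Women with a positive pregnancy test on enrollment or prior to study drug/medication administration".

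**The concern.** The text and the schedule give a site different instructions at Day 21. Sites usually work from the schedule, and one that does so will run no pregnancy test at that visit.

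Day 21 matters because it is where half of the randomised patients, under 1:1 allocation, first receive active drug. A placebo-first woman would start rimegepant on a Day 1 result and would not be tested again until Day 35, after the two-week course. A rimegepant-first woman has serum and urine tests on the day she starts. A pregnancy that became detectable between Day 1 and Day 21 could therefore go unnoticed before first exposure in one sequence only. What is at stake is participant safety and a consistent schedule, not the efficacy comparison.

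**Working it through.** The plan gives no figure to reproduce. The check is a reading of the two schedules against the text, plus day counts.

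**1. Tests and dispensing by visit (Protocol Tables 1 and 2, Sections 3.5.2 and 6.2.2)**

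| Visit | Serum test | Urine test | Laboratory Assessments | LFTs | Supply dispensed |
|---|---|---|---|---|---|
| Baseline (Day 1) | yes | yes | yes | yes | rimegepant or placebo |
| Day 14 | no | no | no | yes | placebo washout, both sequences |
| Day 21 | no | no | no | no | rimegepant or placebo |
| Day 35 | no | yes | yes | yes | open-label rimegepant, if entering the extension |
| Day 63 | no | yes | no | yes | open-label rimegepant |
| Day 91 | no | yes | no | yes | open-label rimegepant |

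Day 21 has no laboratory draw of any kind, so item 5 covers it however lab assessments are defined.

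Dispensings that can contain rimegepant are Days 1, 21, 35, 63 and 91. Four of these five have a pregnancy test at the same visit; Day 21 is the exception.

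**2. Windows (Table 1)**

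- Day 14 ± 2: Days 12 to 16
- Day 21 ± 2: Days 19 to 23
- Day 35 −2/+5: Days 33 to 40

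**3. Last scheduled test to first rimegepant supply**

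- Placebo-first: 21 − 1 = 20 days. Range: 19 − 1 = 18 to 23 − 1 = 22.
- Rimegepant-first: 1 − 1 = 0 days.
- If the placebo-first woman takes her first period 2 tablet the morning after the visit, the interval to first dose is 22 − 1 = 21 days (19 to 23).

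**4. Longest interval between scheduled tests in the double-blind phase**

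- Table 1 as written (Days 1 and 35): 35 − 1 = 34 days. Range: 33 − 1 = 32 to 40 − 1 = 39.
- Day 21 added: the intervals are 20 and 35 − 21 = 14, so the longest is 20 days. The first interval alone runs from 18 to 22 and the second cannot exceed 40 − 19 = 21, so the range is 18 to 22.
- Days 14 and 21 both added: the intervals are 14 − 1 = 13, 21 − 14 = 7 and 35 − 21 = 14, so the longest is 14 days. The first interval is never below 12 − 1 = 11, and visits on Days 12, 23 and 33 give 11, 11 and 10, so the smallest possible longest interval is 11. The largest is 40 − 19 = 21. The range is 11 to 21.

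**5. Effect of the change.** With a Day 21 test done before dispensing, the placebo-first interval in step 3 falls from 20 days to 0. A Day 14 test alone would leave 21 − 14 = 7 days.

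**The case against.** **Item 5 is loosely drafted.** It lists occasions joined by *or* and ends with investigator discretion, so it could be read as a menu, with Table 1 setting the actual visits. That reading leaves the clause on visits without labs with nothing to do. Discretion permits a Day 21 test but does not schedule one.

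**Remote visits are covered.** The COVID-19 provisions in 3.5.2 require a documented negative test for continued participation and before any shipment. They also require local labs at Day 21 when that visit is remote, without saying which. Table 1 footnote (f) limits a shipment to two weeks' supply. This largely stands. The shipment rule sets no limit on how old the test may be, but the gap is mainly one for women who attend Day 21 in person.

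**No eligibility rule is broken.** A reader might infer that inclusion 3d and exclusion 4b oblige a new test before first active dosing. They do not. 3d is a Baseline test, and 4b concerns blinded study drug, active or placebo. Both are met on Day 1 in either sequence. They show the protocol's general approach of testing before drug, but retesting at the period switch rests on item 5.

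**Longer gaps are accepted elsewhere.** The extension allows 63 − 35 = 28 days between tests during continuous rimegepant dosing. That is correct, but each extension dispensing has its own test, whereas Day 21 can be a first exposure with none.

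**Day 14.** A reader might infer an equal failure at Day 14, since its Laboratory Assessments cell is also blank. The documents do not settle this. LFTs are drawn at Day 14, and SAP 6.4.2 lists them under serum chemistry, so the visit is arguably not free of labs. Table 2 does mark the urine test at Days 63 and 91, where only LFTs are drawn, which makes Day 14 look inconsistent. But its supply is placebo for both sequences, so it is not a safety point.

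**Conclusion.** The mismatch at Day 21 is real and minor. Item 5 calls for a urine test there and Table 1 schedules none. As a result, placebo-first women of childbearing potential start rimegepant 20 days (18 to 22) after their last scheduled test, against 0 days for rimegepant-first women. This assumes that the site follows Table 1, that the visit is in person, and that the first active dose is taken on the Day 21 visit, as SAP 6.4.1.3 has it.

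The practical consequence is probably small. The number of women of childbearing potential is not given; Protocol 1.1 cites an average onset age of 63, and SAP Section 1 records early termination for low enrolment. Protocol 4.5 requires two contraceptive methods, and 8.2.2 requires permanent discontinuation once a pregnancy is known.

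A reader might want to state how many pregnancies a Day 21 test would detect. The documents do not support such a figure: they give no detection window, and the yield would also depend on conceptions just before Day 1 that the baseline tests could miss. Nothing here alters the endpoints, sample size or efficacy analyses.

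**What to change.** In Table 1, mark the urine pregnancy test at Day 21, to be completed before dispensing, for all women of childbearing potential. It must apply to both sequences because sites are blinded to sequence. Item 5 needs no change.

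Optionally, mark Day 14 as well, so that the double-blind schedule treats visits with LFTs only in the same way as Table 2.

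The cost is one table mark and one urine test per woman, which the text already calls for, or two of each if Day 14 is included. As the study has ended, the correction serves any reuse of this schedule; the study report can state which rule sites followed at Day 21.
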